7.6 Medical Care of Patients after End of Trial Participation

After completing treatment in this trial, patients will be offered standard of care treatment in accordance with generally accepted medical practice and depending on the patient's individual medical need. Patients will continue to be followed for survival.

8. TRIAL ASSESSMENTS

All trial assessments are considered mandatory for all patients included in the trial, unless otherwise stated. All assessments are to be performed on or about the indicated visit day, i.e., ± 2 days, unless otherwise stated. A slightly longer allowance for routine assessments is permissible in the event of scheduling difficulties associated with weekends, holidays, etc.

8.1 Baseline Characteristics / Eligibility Assessments

8.1.1 Signing of Informed Consent

Prior to any protocol-related procedure, unless such testing was performed previously as part of the routine clinical management of the patient.

- Screening

Note: Informed consent may be obtained outside the 14-day screening period prior to C1/D1

8.1.2 Demographics

To include date of birth, sex, race and ethnicity (as allowed by country)

- Screening

8.1.3 Medical History

To include prior and ongoing medical illnesses and conditions and prior surgical procedures not related to the primary diagnosis.

- Screening
- C1/D1 (prior to dosing)

8.1.4 Tumor Characteristics and Extent of Disease

To include diagnosis and date of initial diagnosis, staging at time of initial diagnosis and at screening, tumor histology, current location of metastases, and date of most recent disease progression, and mutation status.

- Screening

8.1.5 Prior Cancer Treatments

To include prior surgical procedures for the primary diagnosis, as well as prior radiotherapy, chemotherapy and/or biological targeted therapy, investigational treatment, and/or procedures. Include dates of treatments, numbers of cycles, and best response to such treatments.

- Screening
- C1/D1 (prior to dosing)

8.2 Safety Assessments

To be performed within 14 days of C1/D1, unless otherwise specified.

8.2.1 Medication/Procedure Survey

To include all medications taken other than Sym015 and all procedures performed during trial.

For medications: Include generic name or brand name, indication for use, dose and frequency, route of administration, start and stop dates or if ongoing at 1M FUP Visit. For procedures: Include date and reason for procedure.

- Starting from the date of Screening
- Until the date of the 1M FUP

8.2.2 Adverse Events Survey

For details about (S)AEs and (S)AE reporting, refer to Section 9.

- Starting from signing of informed consent for participation in the trial
- Until the date of the 1M FUP

Note: Patients who sign informed consent and are subsequently deemed to be screening failures will be followed for the occurrence of SAEs/AEs until it is determined that they will not be participating in the trial

8.2.3 Dose-Limiting Toxicities Evaluation (Part 1 Only)

For details about AEs meeting DLT criteria, refer to Section 9.5.

- Starting from the first dose of trial drug (C1/D1)
- Reported during Cycle 1 with a final assessment 14 (± 2) days after the last dose of Cycle 1 or prior to dosing on C2/D1

8.2.4 Vital Signs and Body Weight

To include temperature, heart rate, blood pressure, and body weight

- Screening
- Prior to each dosing
- EOT
- 1M FUP

- As clinically indicated

8.2.5 Performance Status

To be assessed by ECOG PS score.

- Screening
- Day 1 of each cycle (prior to dosing)
 - Does not need to be assessed prior to C1/D1 if assessed during screening \leq 7 days from C1/D1
- EOT
- 1M FUP
- As clinically indicated

8.2.6 Physical Examination

To include evaluation of the following at Screening: General appearance, skin, head, ears, eyes, nose, throat, neck/thyroid, chest, cardiovascular system, abdomen, musculoskeletal system, lymph nodes, neurologic status, and mental status; include height (without shoes, rounded to nearest centimeter). Thereafter, a targeted physical examination may be performed as indicated.

- Screening
- Day 1 of each cycle (prior to dosing)
 - Does not need to be performed prior to C1/D1 if performed during screening \leq 7 days from C1/D1
- EOT
- 1M FUP
- As clinically indicated

8.2.7 Electrocardiogram

To include standard 12-lead electrocardiogram (ECG). The Investigator, or qualified designee, should document the evaluation of the ECG, including specification of any abnormality as clinically significant or not clinically significant.

- Screening
- EOT
- As clinically indicated

8.2.8 Echocardiogram or Multi-Gated Acquisition Scan

Patients will be scheduled for a transthoracic echocardiogram (ECHO) at baseline to exclude enrollment of patients with insufficient heart function; alternatively, a radionuclide angiography (Multi-Gated Acquisition [MUGA] scan) of the heart may be performed.

- Screening
- In the event of cardiac symptoms (e.g., shortness of breath, edema) an ECHO or MUGA is to be scheduled as soon as possible
- As otherwise clinically indicated

8.2.9 Laboratory Assessments and Pregnancy Test

All routine laboratory analyses will be performed at a laboratory facility local to the trial site. Results must be available and assessed prior to each dosing of Sym015.

Sponsor or designee must be provided with a list of trial site laboratory normal ranges for all required parameters prior to screening of the first patient at the site. Likewise, any change in laboratory normal ranges during the trial should be forwarded to the Sponsor or designee promptly during the trial.

Blood samples will be taken at all scheduled visits and will be analyzed for the following parameters as per [Table 8](#) and as clinically indicated:

Table 8 Schedule of Safety Blood and Urine Samples

Sample Analysis	Screening	Cycle 1				Cycles Thereafter		EOT	IM FUP
Day within Cycle		D1	D3 D8	D15	D22	D1	D15		
Hematology Panel	X	X ¹	X	X	X	X	X	X	X
Biochemistry Panel	X	X ¹	X	X	X	X	X	X	X
Coagulation Panel	X	X ¹	X	X	X	X	X	X	X
Urinalysis	X	X ¹		X		X		X	X
Pregnancy Test	X							X	

Abbreviations (in alphabetical order): D, day; EOT, End of Treatment Visit; 1M FUP, 1-Month Follow-up Visit

1) Does not need to be performed prior to C1/D1 if performed during screening \leq 7 days from C1/D1

8.2.9.1 Hematology Panel

To include complete blood count with differential, ANC, and platelet count.

- Screening
- Cycle 1
 - Weekly (prior to Sym015 administration on days of dosing)
 - Does not need to be performed prior to C1/D1 if performed during screening ≤ 7 days from C1/D1
 - Day 3
- Each cycle thereafter
 - Prior to each dosing
- EOT
- 1M FUP
- As clinically indicated

In the event of hematologic toxicity, the evaluation frequency should be increased to include additional evaluations between scheduled assessments, as clinically indicated.

8.2.9.2 Biochemistry Panel

To include sodium, potassium, chloride, bicarbonate or carbon dioxide, blood urea nitrogen (BUN), creatinine, glucose, bilirubin [total and direct], AST, ALT, ALP, calcium, magnesium, phosphorus, albumin, total protein, uric acid, amylase, lipase, and creatine kinase (fasting not required). Clinically significant electrolyte abnormalities should be corrected prior to dosing.

- Screening
- Cycle 1
 - Weekly (prior to Sym015 administration on days of dosing)
 - Does not need to be performed prior to C1/D1 if performed during screening ≤ 7 days from C1/D1
 - Day 3
- Each cycle thereafter
 - Prior to each dosing
- EOT

- 1M FUP
- As clinically indicated

In the event of significant biochemistry abnormalities, the evaluation frequency should be increased to include additional evaluations between the scheduled assessments, as clinically indicated. In the event of creatine kinase abnormalities, isoenzyme analysis should be performed.

8.2.9.3 Coagulation Panel

To include prothrombin time, PTT and INR.

- Screening
- Cycle 1
 - Weekly (prior to Sym015 administration on days of dosing)
 - Does not need to be performed prior to C1/D1 if performed during screening ≤ 7 days from C1/D1
 - Day 3
- Each cycle thereafter
 - Prior to each dosing
- EOT
- 1M FUP
- As clinically indicated

8.2.9.4 Urinalysis

Multi-parameter chemical test strips are acceptable and should include assessment of: specific gravity, pH, protein, glucose, ketones, occult blood, leukocyte esterase, nitrite, bilirubin, and urobilinogen.

- Screening
- Cycle 1
 - Prior to each dosing
 - Does not need to be performed prior to C1/D1 if performed during screening ≤ 7 days from C1/D1
 - Day 1 of each cycle thereafter (prior to dosing)

- EOT
- 1M FUP
- As clinically indicated

8.2.9.5 Pregnancy Test

Serum human Chorionic Gonadotropin (β -hCG) at screening, urine β -hCG thereafter, in women of childbearing potential.

- Screening
- EOT
- As clinically indicated

Women are considered of childbearing potential unless they have been hysterectomized, have undergone tubal ligation or have been postmenopausal for at least one year.

8.3 Disease Assessments

8.3.1 Disease Status Evaluation by CT or MRI

The anti-tumor activity of Sym015 will be assessed by the Investigator, or qualified designee, according to RECIST v1.1 (29). Refer to [Appendix 1](#).

Patients will undergo imaging by CT or MRI of neck, chest, abdomen and pelvis as indicated based on tumor type and clinical judgment in order to follow the underlying malignancy. The use of CT or MRI must be consistent per patient throughout the trial. Use of contrast is preferred but is at the discretion of the Investigator, as medically indicated.

- Screening

Note: A CT/MRI performed within 28 days prior to Day 1 may be used for evaluation of eligibility and as baseline scan, provided that the CT/MRI has been performed according to the protocol requirements

- EOC2 and end of every second cycle thereafter, i.e., EOC4, EOC6, EOC8, etc.

Note: May be performed at any time during the week prior to Day 1 of the next cycle, including Day 1 of the next cycle, prior to dosing (provided results are available prior to study drug administration)

- Suspected PD (as soon as possible)
- At least 28 days following an OR (PR, CR)
- EOT (if >3 weeks since previous CT/MRI)

- At 1M FUP (if PD was not documented before or at EOT)

If PD is documented at any time, no further disease assessments will be required. Patients with documented PD will be discontinued from Sym015 so that alternative management of their malignancy may be considered.

To be assigned a status of PR or CR, changes in disease status must be confirmed by repeat imaging studies performed no less than 28 days (4 weeks) after the criteria for response are first met. In the case of SD, follow-up measurements must have met the SD criteria at least once after trial entry at a minimal interval in general no less than 6-8 weeks from first dose of Sym015.

Imaging data (imaging studies and derived assessments) will be stored by the sites and will be available upon request for potential review by the Sponsor or an independent radiology reviewer. For Part 2 only: In addition, imaging studies will be sent to an imaging facility for storage in order to ensure central availability and readiness for read at a future time upon Sponsor or Health Authority request.

For all imaging time points, the following will be recorded as per RECIST v1.1: Target lesions including size, location, and type (nodal/non-nodal); sum of diameters of target lesions; any new lesions noted during trial, including size, location, and type (nodal/non-nodal); final response assessment at each visit (PD, SD, PR, CR or Not Evaluable [NE]).

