5.3.4 Treatment

On the day of the first scheduled Sym015 infusion (C1/D1) and prior to the start of infusion (SOI), the Investigator must assess whether any changes have occurred in the clinical state of the patient, which would exclude the patient from the trial.

Sym015 will be administered on a Q2W schedule by IV infusion:

- Q2W dosing: Day 1 and Day 15 of each 28-day cycle (\pm 2 days)

There will be no intra-patient dose-escalation.

For all patients, the dose to be administered and the dosing schedule will be documented on the Screening and Allocation Form.

In the event of toxicity due to Sym015, dosing may be delayed, and/or the dose may be reduced, as described in Section [7.1.4](#).

Treatment will continue until unacceptable toxicity or other conditions preventing further treatment, progressive disease (PD), termination of the trial, or patient's decision to withdraw.

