5.3.6 Flow Chart – Schedule of Assessments

Schedules of assessments are provided in the trial flow charts in [Table 3](#) (Part 1 and Part 2 Basket Cohort) and [Table 4](#) (Part 2 NSCLC Cohorts).

All efforts should be made to perform assessments as close as possible to the scheduled time points. Visit windows are included in the flow chart.

The projection of visit days within each cycle must be made from Day 1 of the respective cycle. Furthermore, each new cycle must be initiated as soon as possible after completion of the previous cycle in order to achieve the Q2W dosing schedule.

Table 3 Flow Chart: Schedule of Assessments (Part 1 and Part 2 Basket Cohort)

Pre-Treatment Period		Treatment Period ¹										Post-Treatment Period ²	
	Screening	Cycle 1				Cycle 2, 4, 6 etc.				Cycle 3, 5, 7 etc.		EOT	1M FUP ²
Day within Cycle Visit Window (± days)	D-14 to D-1	D1	D3	D8 (±2)	D15 (±2)	D22 (±2)	D1 (±2)	D15 (±2)	End of Cycle	D1 (±2)	D15 (±2)	≤ 10 d following the decision of trial treatment withdrawal	1 month after last dose of trial treatment (30+7d)
Informed Consent	X												
Baseline Characteristics/Eligibility ³	X	X											
Safety Assessments													
Medication/Procedure Survey	X	X			X		X	X		X	X	X	X
(S)AE Survey and Reporting	X	X	X	X	X	X	X	X	X	X	X	X	X
DLT Evaluation ⁴		X	X	X	X	X	C2 only						
Part 1/Dose-Escalation only													
Vital Signs and Body Weight	X	X			X		X	X		X	X	X	X
ECOG PS ⁵	X	X ⁵					X			X		X	X
Physical Examination ⁵	X	X ⁵					X			X		X	X
ECG ⁶	X											X	
ECHO or MUGA scan ⁷	X												
Safety blood samples ^{5,8}	X	X ⁵	X	X	X	X	X	X		X	X	X	X
Urinalysis ^{5,8}	X	X ⁵			X		X			X		X	X
Pregnancy Test	X											X	
Disease Assessments													
Disease Status Evaluation by CT/ MRI ⁹	X								X			X ¹⁰	X ¹⁰
Tumor Marker Evaluation ¹¹	X								X			X	X
Archival Tumor Tissue (may include pre-screening by liquid bx) ¹²	X												
Tumor Biopsy ¹³	X ¹³							C2 only ¹³					
Additional Assessments													
PK Samples ¹⁴		X	X	X	X		X	X		X	X	X	X
ADA Sample ¹⁵		X					C2 only ¹⁵			X		X	X
Skin Biopsy ¹⁶	X							C2 only ¹⁶					
Part 1/Dose-Escalation only													
Biomarker Blood Sample ¹⁷	X							C2 only ¹⁷				X	
Trial Treatment													
Sym015 Premedication ¹⁸		X			X		X	X		X	X		
Sym015 Infusion		X			X		X	X		X	X		
Post-Infusion Monitoring		X			X		X	X		X	X		

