 - The first CT/MRI assessment for response is done at the EOC2 and thereafter repeated at the end of every second cycle (EOC assessments may be performed at any time during the week prior to Day 1 of the next cycle, including Day 1 of the next cycle prior to dosing, provided results are available prior to study drug administration)
 - In the event of suspected PD, a CT/MRI is to be performed as soon as possible.
 - In the event of CR/PR, a confirmatory CT/MRI is to be performed no earlier than 28 days after the first assessment of CR/PR.
 - A CT/MRI at EOT should only be performed if the previous CT/MRI has been performed >3 weeks before. A CT/MRI scan at 1M FUP should only be performed if no CT/MRI documents PD before or at EOT.
- 9) **Tumor Biopsy:** Recent or newly performed biopsies are mandatory at screening; it is permissible to perform the screening procedure outside the 14-day screening period provided informed consent for the trial has been obtained. EOC2 tumor biopsies (coinciding with time of first response assessment) or upon PD, whichever occurs first, are optional.
- 10) **PK Samples:** Extended PK sampling for PK profiling will be done starting C1/D1. Refer to Table 9 for details.
- 11) **Genomic/Biomarker Blood Sample:** It is permissible to obtain the screening sample outside the 14-day screening period provided informed consent for the trial has been obtained. Subsequent samples to be obtained: EOC2 (coinciding with time of first response assessment) or upon PD, whichever occurs first; EOT (if after EOC2; need not repeat if patient is discontinuing at the EOC2 or if a sample was obtained upon PD). If a tumor biopsy is collected at the same time point as the biomarker blood sample, the biomarker blood sample should be collected prior to collecting the tumor biopsy.
- 12) **Premedication:** Mandatory prior to each dose of Sym015 during Cycle 1; may be withdrawn after Cycle 1 on a patient-by-patient basis if the patient is without evidence of infusion related reactions. Refer to Section 7.2.1 for details.

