7.1.4.2 Dose-Delays for Sym015-Related or Disease-Related Toxicities

Clinical judgment will be used when determining whether it is advisable to continue a patient on to the next dosing. In order to dose a patient, the following criteria must be met:

- ANC $> 1.0 \times 10^9/L$ (1000/mm³)
- Platelet count $> 60 \times 10^9/L$ (60,000/mm³)
- Any ongoing AEs should NOT meet the criteria for DLT, during the DLT observation period
- Any ongoing AEs, assessed as possibly, probably, or related to Sym015, should have either ameliorated to \leq Grade 1 severity, returned to baseline status, or resolved with the exception of Grade 2 clinical events that are being adequately controlled with best supportive care (e.g., nausea, vomiting, diarrhea, fatigue) and asymptomatic laboratory abnormalities that are considered clinically insignificant or that are resolving with medical therapy

Should any one of the criteria above not be met, dosing of Sym015 must be delayed until the patient meets the above criteria. All per protocol assessments must be done.

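### Routine scans are tied to cycles rather than to the calendar, so a dose delay that moves the next cycle can also move the scan, with stable disease beyond 4 months most exposed

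*Protocol*

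**What the plan says.** - **Scan schedule.** Protocol section 8.3.1 places routine on-treatment imaging at "EOC2 and end of every second cycle thereafter, i.e., EOC4, EOC6, EOC8, etc". The window reads "May be performed at any time during the week prior to Day 1 of the next cycle", extending to that Day 1 before dosing if results are ready. Table 4 footnote 8 has the same rule ("EOC assessments may be performed at any time during the week prior to Day 1 of the next cycle"), and Table 3 footnote 9 also uses the week before the next Day 1.
- **Cycle clock.** Section 5.3.4 doses on "Day 1 and Day 15 of each 28-day cycle". Section 5.3.6 adds: "The projection of visit days within each cycle must be made from Day 1 of the respective cycle".
- **Dose delay.** Section 7.1.4.2 states: "Should any one of the criteria above not be met, dosing of Sym015 must be delayed until the patient meets the above criteria". It gives no maximum, and the withdrawal list in section 6.3.1 gives none either. The only figure, more than 2 weeks because of Grade 3 or worse toxicity, belongs to the DLT definition in section 9.5.1, which applies to Part 1 only.
- **During a delay.** Section 7.1.4.2 also says: "All per protocol assessments must be done".
- **Scans not tied to a cycle.** Section 8.3.1 also orders imaging for suspected progression, at least 28 days after a response, at end of treatment and at the 1-month follow-up, with conditions on the last two.
- **Endpoints.** Section 10.5.1 lists duration of response, SD for more than 4 months, TTP on radiological evidence, PFS and OS as secondary. The Part 2 primary endpoint (section 10.4.2) is confirmed objective response, whenever it occurs in the trial.

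**The concern.** The routine scan has no date of its own. It is defined by the next cycle's Day 1, and that day can slip. A patient whose dosing is held may then be imaged later than a patient on schedule with the same disease, so progression that is not clinically apparent is documented later.

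At stake are the endpoints dated by scans. TTP and PFS would depend partly on dosing history. SD beyond 4 months is a fixed cut-off that lies just after a scheduled scan, so a modest slip can change a patient's category with no change in disease. There is no control arm to share the effect.

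**Working it through.** The protocol states no figure for this point, so there is none to reproduce.

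**1. Nominal scan days.** With 28-day cycles, the end of cycle k is day 28k: day 56 (Cycle 2), day 112 (Cycle 4), day 168 (Cycle 6). With the 7-day window, the Cycle 4 scan falls on day 105-112. At 365.25/12 = 30.44 days per month, that is 3.45-3.68 months.

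**2. The 4-month cut.** 4 × 30.44 = 121.75 days. The slip needed to carry the Cycle 4 scan past it is 121.75 − 112 = 9.75 days (scan at the end of the window) to 121.75 − 105 = 16.75 days (scan at the start). In whole days that is 10-17. A 14-day slip puts an end-of-window scan on day 126 (4.14 months), and a 28-day slip on day 140 (4.60 months).

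**3. Effect on the proportion progression-free beyond 4 months.** Assumptions, none given in the protocol: exponential time to progression with true median M of 2, 4 or 6 months; 30% of patients delayed once by 14 days before the Cycle 2 scan; scans at the end of the window; progression dated at the scan that shows it. Write S(t) = 2^(−t/M).
- On schedule, progression is dated after day 121.75 only if it occurs after day 112, giving S(112).
- With scans on days 70 and 126, this happens if it occurs after day 70, giving S(70).
- Mixture: 0.7·S(112) + 0.3·S(70).

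| True median | S(112) | S(70) | Mixture | Rise (points) |
|---|---|---|---|---|
| 2 months | 27.9% | 45.1% | 33.1% | 5.1 |
| 4 months | 52.9% | 67.1% | 57.1% | 4.3 |
| 6 months | 65.4% | 76.7% | 68.8% | 3.4 |

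A simulation of the same cases agrees to about 0.1 point (33.0%, 57.2%, 68.7%). If half of progressions are found within 7 days by a suspected-progression scan, the simulated figures go from 27.5% to 30.0%, from 52.5% to 54.6% and from 65.0% to 66.7%, about half the rise.

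**4. Effect on mean detection time.** The on-schedule mean is 56/(1 − S(56)). With a 14-day slip it is 70 + 56·S(70)/(1 − S(56)). For a 2-month median, S(56) = 0.5285, so the means are 118.8 and 123.5 days, a difference of 4.7 days in a delayed patient. With 30% delayed, 0.3 × 4.7 = 1.4 days. Across the three medians, with and without early detection, the simulated shift is 0.3-1.4 days. If every patient is delayed once, by 14 or 28 days, it is 0.9-10.9 days.

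**5. Direction.** A shifted grid can also find progression sooner. Progression on day 60 is seen on day 112 on schedule, but on day 70 after a 14-day slip. The observed median can therefore fall: with a 4-month true median and every patient delayed by 14 days, it moves from 5.52 to 4.14 months.

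**The case against.** The strongest reply is that the key step is inferred. No sentence says that a held dose lengthens the cycle. Cycles are nominally 28 days, assessments are still required during a delay, and Table 9 footnote 1 provides for a visit at which the drug is paused. For a missed Day 15 dose in particular, a calendar reading is open. This stands in part: a reader might infer that every dosing delay postpones the scan, and the text does not support that. But the duty to perform assessments does not date the scan, and the Table 9 footnote concerns PK samples. Where the next Day 1 does move, the scan window is defined by it. If sites may read the rule either way, that itself needs settling.

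Several stronger readings do not hold:
- **Delay is unlimited everywhere.** The Part 1 DLT criterion is an exception.
- **Held patients are those most likely to be progressing.** This leans on the heading of section 7.1.4.2. Its adverse-event criteria concern drug-related events, so disease-related problems trigger a listed hold mainly through blood counts.
- **Progression goes unseen throughout a hold.** Suspected-progression and end-of-treatment scans do not depend on the cycle.
- **PFS lengthens by about 11 days.** That needs a 28-day hold in every patient counted, a 2-month median and no early scans.

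The consequence is also limited. The affected endpoints are secondary and descriptive, section 10.1 plans no hypothesis test, and with no control arm delays cannot differ between arms.

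**Conclusion.** The point holds in a limited form. Routine scans follow the cycle, the cycle can slip, and the protocol does not keep the scan on the calendar. On average this lengthens TTP and PFS, though not for every patient or every median, and the mean effect is small: 0.3-1.4 days if 30% of patients are delayed once by 14 days.

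The exposed endpoint is SD beyond 4 months, because the Cycle 4 scan lies 10-17 days before the cut. Under the same assumption the observed proportion rises by about 3-5 points, or about half that with half of progressions caught early. Three to five points is about one patient in a cohort of 20-25. Delay frequency, true median and the share caught early are all assumptions. So is the use of time to documented progression to stand for SD beyond 4 months.

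A reader might infer that the main result is affected. It is not biased in this way: confirmed response has no time limit, and OS does not depend on scan dates. This is an inexpensive improvement to secondary endpoints, not a threat to the trial's conclusion.

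**What to change.** In section 8.3.1, Table 3 footnote 9 and Table 4 footnote 8, schedule routine scans every 8 weeks from C1/D1, with a window of −7 days and a small stated plus window. State that this applies regardless of dose delays or interruptions, until progression or new anticancer therapy. Keep the suspected-progression, confirmation, end-of-treatment and 1-month follow-up scans as they are.

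Patients on schedule keep the same nominal scan days (56, 112, 168), and a dosing delay then shifts the scheduled scan by 0 days. The cost is a wording amendment and an occasional scan visit separate from a dosing visit. No dosing or dose-delay rule changes.
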